All participants report some demographic information, their current affective state (Positive and Negative Affect Scales-PANAS (120), provide information on a broad-band personality measure (Brief Multidimensional Personality Questionnaire- bMPQ); (121) and supplemental measures of trait affectivity relevant to individual differences in anxiety including the Intolerance of Uncertainty Inventory, (122), and the Anxiety Sensitivity Inventory (123). Individual differences in depressive symptoms will also be recorded Center for Epidemiologic Studies Depression Scale Revised (CESD-R; 125) and the Depression Anxiety Stress Scale-21 (DASS-21).

These measures are available to serve as covariates to increase power to test for focal effects on relevant outcome measures. They are also available as possible individual difference moderators in supplemental analyses. After completing the self-report measures, participants schedule their first experimental session. Participants are randomized to either a nicotine deprived or non-deprived condition and instructed to abstain from all nicotine containing products for 24 hours prior to their nicotine deprived session or to continue their normal pattern of smoking prior to their non-deprived session.

Finally, participants receive brief cessation counselling, schedule their experimental visits and quit date, and are provided with verbal and written instructions about the 3-week daily EMA survey that begins one week before their quit date.

C2.3: Laboratory Experimental Session(s)

All participants complete the cued threat task (NPU; see section C3 below) in each of two separate experimental sessions. Their first session is either nicotine deprived and non-deprived in a counterbalanced order, the final is 2 weeks post-quit. The deprived group completes their first experimental session the day after the start of their quit attempt, and the non-deprived group completes it before the start of their quit attempt. Data across the two experimental sessions will be used to provide sensitive within-subjects tests of deprivation effects on startle potentiation measures of stress neuroadaptation (Aim 1) and to address all subsequent Aims (2-4).

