On arrival at the laboratory for each of both experimental sessions, participants report the time of their last cigarette and have their CO level measured. For the nicotine deprived session, participants must self-report no tobacco use within the last 24 hours and have a CO level < 6ppm. If they fail to abstain from tobacco products, they are rescheduled once. Our experience across many previous nicotine deprivation studies (33,58,86,126,127) with similar monetary incentives suggest fewer than 5% of participants will fail to abstain for their first scheduled deprivation session and require rescheduling. The majority of these participants will succeed in their second attempt. If they fail to abstain a second time, their participation is discontinued. These estimates are likely conservative given that the current sample is motivated to quit. As such, we do not expect attrition due to failure to abstain to bias the sample substantially. Following this, all participants complete a measure of their current affective state (PANAS), smoking urge (QSU) and withdrawal (WSWS) described earlier.

On completion of the task, participants receive brief cessation counseling, and combo NRT or placebo NRT according to their randomized treatment condition (see below).

C2.4 Treatment Groups

Participants are **randomly** assigned to one of two treatment groups: combination NRT (patch and lozenge) vs placebo NRT, both accompanying by motivational enhancement counseling. Due to the different visit calendars required for the two arms, study staff are not blinded to treatment arm.

Combination NRT: Participants assigned to the combo NRT arm will use 21-mg nicotine patches for 2 weeks. Participants will be given instructions on how to use the patch consistent with recommended use (20). They will be told to apply one patch each morning to a non-hairy body surface between the neck and waist. Moreover, they will be encouraged to report any side effects promptly so that steps may be taken to facilitate effective medication use (e.g., use of cortisone cream for skin reactions). Participants will also be provided with nicotine lozenges (2-mg). Participants will be instructed on recommended lozenge use (20). They will be encouraged to use at least one piece every 1-2 hours and to establish a consistent schedule to prevent rather than ameliorate craving and/or withdrawal symptoms. Both NRT patches and lozenges are over-the-counter “Up and Up” brand (purchased through Target.com).

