C2.4.1: Design Considerations and Justification: We discussed our careful considerations regarding our focus on the Cessation period and the use of this surrogate endpoint during a smoking cessation attempt in section A5 earlier. We also carefully considered an alternative design where we measured negative affective response during a single session of NRT administration to deprived smokers in the laboratory rather than at one week into a quit attempt. Although this alternative would be simpler, it may fail to capture a number of critical elements that are relevant to real-world quit attempts. In particular, the affective experience is likely quite different during a temporary deprivation period vs. a similar duration of deprivation in the context of an intended permanent cessation of use. Furthermore, the effects of deprivation likely vary over time during the cessation attempt as regulatory resources become drained and homeostatic adaptation processes are recruited (104,129–131). Our current design indexes negative affect both early in deprivation (during the pre-quit deprived session) and after one week of cessation. In addition, the 2 week quit period provides the opportunity for detailed real world measurement of stressor-affect, stressor-urge, and stressor-smoking relations via EMA (see below) that would not be available with the single NRT administration in the laboratory. We believe these benefits justify our current design.

Participants are instructed to continue NRT even if they fail to maintain complete abstinence during their quit attempt. There is evidence that participants benefit from reduced smoking on NRT even if full abstinence is not obtained or maintained (20). This procedure will allow all participants to be included in analyses of EMA cessation measures. Furthermore, analyses of the cued threat task that is administered at one week post-quit can retain all participants but include regressors/covariates to model the amount of smoking (and medication use) during the first week.

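### Smokers who twice fail the abstinence check are removed after randomisation, from the deprived group only, and the plan does not follow them up or say how they are counted

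*Combined protocol and SAP*

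**What the plan says.** Under C2.2, at the screening visit, "Participants are randomized to either a nicotine deprived or non-deprived condition". C2.3 then sets the calendar: "The deprived group completes their first experimental session the day after the start of their quit attempt", whereas "the non-deprived group completes it before the start of their quit attempt". Only the first of these sessions has an entry test: "For the nicotine deprived session, participants must self-report no tobacco use within the last 24 hours and have a CO level < 6ppm". One reschedule is allowed. After that, "If they fail to abstain a second time, their participation is discontinued".

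C2.3 recognises this attrition. It cites the laboratory's earlier nicotine deprivation studies for the expectation that "fewer than 5% of participants will fail to abstain for their first scheduled deprivation session". It expects most of those to pass at the second attempt, calls the estimate conservative because the sample wants to quit, and foresees no substantial bias. It places dispensing of active or placebo product after the task.

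C2.4.1 tells participants to keep using the product after a lapse and adds: "This procedure will allow all participants to be included in analyses of EMA cessation measures". The Statistical Considerations section defines no analysis population and does not say how discontinued smokers enter Aims 2 to 4.

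**The concern.** The deprived session falls one day into the quit attempt, so a smoker who fails the check has smoked at the very start of the period that Aim 3 measures (amount smoked, point prevalence and continuous abstinence to two weeks). In the deprived group, two such failures end participation, and the later momentary (EMA) reports and the two-week CO visit are lost along with one startle session. A non-deprived smoker who smokes on the same day stays in and is counted as smoking.

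If startle predicts smoking, as Aim 3 supposes, the rule trims the high-startle end of one randomised group. That would tend to shrink the deprivation contrast in Aim 1 and restrict the range of the predictor in Aim 3. The sentence in C2.4.1 about including everyone is also not true of these smokers, because they leave before any product is dispensed.

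**Working it through.** **Inputs from the protocol.** First-failure rate below 5%, and more than half of those succeed on the second attempt (C2.3). Total N is 300, and N = 142 gives 90% power at effect size 0.10 (C4.3).

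**Assumptions, not in the documents.** Allocation to deprivation is 1:1, so 150 per group. Alpha is 0.05. True two-week abstinence is 40% (range 30% to 50%), and everyone removed would have been smoking. The correlation r between startle and the liability to fail is 0.3 to 0.5. For scale, the plan's effect size read as a squared correlation gives r = √0.10 ≈ 0.32, so 0.5 is generous.

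**1. The plan's sample size.** Reading 0.10 as Cohen's f² with 3 numerator df, the large-sample noncentrality for 90% power is 14.17, and 14.17/0.10 = 141.7, so 142 is reproduced (exact noncentral F gives 146). On that basis power is 90.9% at 150 per treatment group. It is 90.5% at 148, that is, with 4 losses split over the two groups. Power is not the issue.

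**2. Number removed at the plan's rates.** d < 0.05 × 0.50 = 0.025, and 150 × 0.025 = 3.75. So fewer than 4 deprived smokers are removed, against none under this rule in the non-deprived group.

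**3. Abstinence among those retained.** p/(1 − d) = 0.40/0.975 = 0.410, an overstatement of 1.0 point (0.8 at p = 30%, 1.3 at p = 50%).

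**4. Shift in mean startle in the deprived group.** Removing the top share d of a normal liability moves the startle mean by −r × φ(z)/(1 − d). At d = 0.025, φ(1.960) = 0.0584 and 0.0584/0.975 = 0.060. Multiplying by 0.3 and 0.5 gives −0.02 to −0.03 SD.

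**5. If failure is more common than forecast.** The rates below the first row are assumed.

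| Removed, d | Lost of 150 | 40% abstinence reads | Startle shift (SD) |
|---|---|---|---|
| 2.5% (plan's upper limit) | 3.75 | 41.0% | −0.02 to −0.03 |
| 5% | 7.5 | 42.1% | −0.03 to −0.05 |
| 10% | 15 | 44.4% | −0.06 to −0.10 |
| 20% | 30 | 50.0% | −0.10 to −0.18 |

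**6. The two sections side by side.** C2.4.1 rests its inclusion statement on lapsers continuing their product. C2.3 gives out that product only after the task. A twice-failing deprived smoker has nothing to continue and is no longer in the study, so the inclusion statement cannot cover that person. Neither section says whether rescheduling moves the quit date. If it does, a first failure is a postponed quit and day 1 of the two-week window has to be redefined. If it does not, both failures fall inside the window.

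**The case against.** C2.3 already identifies this attrition, puts a number on it and judges it small. On that number the effect is small. The check also has a purpose: a smoker who has not abstained cannot supply a deprived startle score. Both points stand.

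A reader might infer several stronger things that the documents do not support.

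- *That the plan flatly contradicts itself by promising to analyse everyone.* The C2.4.1 statement concerns lapsers told to continue their product. Its wording is too broad for smokers removed earlier and needs reconciling, but it is not a general promise.
- *That the comparison of nicotine replacement with placebo is biased.* Removal comes before dispensing, and the same rule applies whatever the treatment. Specific Aims places treatment assignment after the laboratory measure, without an exact time. Exclusion after randomisation is certain only for the deprivation factor.
- *That inflated abstinence distorts a planned test.* No aim compares abstinence between deprived and non-deprived smokers. The routes to harm are selection in Aim 1 and range restriction in Aim 3.
- *That 10% to 20% will be removed.* No passage gives such a rate. The forecast does come from earlier deprivation studies, and C2.4.1 itself argues that "the affective experience is likely quite different during a temporary deprivation period" compared with an intended permanent quit. But that remark is about affect, not about success in abstaining for a day. It is a reason for caution about the forecast, not evidence of a higher rate.

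Some wording in C2.3 and in the Aim 1 analysis still describes every participant as having a deprived session, in which case the rule would not be one-sided. The visit calendar in C2.3 and the task description in C3 describe two groups, and this point follows them.

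**Conclusion.** The point holds as a cheap improvement, not as a threat to the trial's main conclusions. The rule acts after randomisation to deprivation, on one group only, and on behaviour that overlaps the Aim 3 outcome. It discards follow-up that existing procedures could collect. At the plan's own rates the cost is fewer than 4 of about 150 smokers, about 1 point of abstinence in the deprived group and 0.02 to 0.03 SD of startle, on the assumptions listed above. The effect grows only if failure exceeds the forecast, and discarded follow-up cannot then be recovered. The direction of the startle shift depends on the trial's own hypothesis being right. That the removed smokers are those most prone to relapse is a reasonable inference, not something the documents state.

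**What to change.** 1. Reconcile C2.3 with C2.4.1, and state whether rescheduling moves the quit date and which date starts the two-week window. Which rule governs the task and study medication is for the sponsor to decide.
2. Under whichever rule is kept, continue EMA and the two-week CO visit for these participants. Keep them in the Aim 3 and 4 smoking outcomes as randomised, using their observed smoking.
3. Treat first-session startle as missing for them. This alone does not remove the selection: Aim 1 still has the same selected deprived sample, and models with startle as regressor still drop these smokers. So add a sensitivity analysis, by multiple imputation or a likelihood-based method, using baseline dependence, withdrawal and affect measures and the two-week startle score.
4. Report the number removed by randomised group.

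The cost is protocol wording, follow-up of a handful of extra participants through procedures already running, and one added sensitivity analysis.

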Participants assigned to the placebo NRT arm receive identical instructions. However, the placebo NRT is “Altoids” brand Spearmint mints (purchased through Amazon.com) and custom-made placebo patches manufactured by American Custom Technologies. The placebo patches are identical in appearance to the real patches except for the absence of the faint stamp reading “21 mg nicotine” on the active product.

Both placebo and active NRT lozenges are removed from their original packaging and repackaged in amber medication vials, to assist with the believability of the placebo manipulation. Similarly, both placebo and active patches are removed from their original packaging and distributed to participants in 2”x3” reclosable food-grade storage baggies.

Medication use for both groups during the two weeks of medication use will be monitored by daily reports via Ecological Momentary Assessment methods (see **Ecological Momentary Assessment** section below).

Counselling: Participants receive 30 minutes of in-person counseling at three points through their participation in the study: during their screening session approximately one week before the start of their quit attempt, 24-hours into their quit attempt, and at the end of their follow-up visit to the laboratory at two weeks into their quit attempt.

At their final visit, participants, if interested, are also put in touch with the Wisconsin Tobacco QuitLine’s program (<http://www.ctri.wisc.edu/quitline.htm>). This final visit represents our last contact with the participant and provides an ideal opportunity to reinforce successful quit attempts or encourage a new quit attempt if needed for both treatment groups. Although not part of the scientific protocol per se, we provide this final counseling session at the end of this visit to further aid our participants in their attempt to maintain smoking abstinence.

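### Participant masking is not secured in the NRT arm: active patches carry a faint 21 mg nicotine stamp that placebo patches lack, and no treatment guess is collected

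*Combined protocol and SAP*

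**What the plan says.** All of the product description is in section C2.4 (Treatment Groups) of the combined protocol and SAP.

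- **Patch appearance.** The custom-made placebo is described as "identical in appearance to the real patches except for the absence of the faint stamp reading"; the stamp gives the drug and strength, 21 mg nicotine, and is found on active patches only.
- **Repackaging.** Lozenges and mints go into amber vials "to assist with the believability of the placebo manipulation". In the same way, "both placebo and active patches are removed from their original packaging and distributed to participants in 2”x3” reclosable food-grade storage baggies".
- **Handling.** On patch use by participants: "They will be told to apply one patch each morning to a non-hairy body surface between the neck and waist". The period is two weeks, and the placebo arm gets the same instructions.
- **Oral product.** In the control arm, "the placebo NRT is “Altoids” brand Spearmint mints".
- **Staff.** The only explicit statement on blinding is that "study staff are not blinded to treatment arm".

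No step to cover, remove or imitate the stamp is described. The measures listed for the visits (C2.2, C2.3, C2.6), the EMA survey (C2.5) and the Statistical Considerations contain no question on which treatment the participant believes they received.

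**The concern.** The purpose given for the repackaging shows that participants were meant to find the placebo credible. The one visible difference that the plan admits between the patches names the drug and its strength, and it sits on the item that the participant handles every day.

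Aim 4 depends on the randomized comparison of combination NRT with placebo NRT, and it attributes any difference to treatment of withdrawal. Many of its outcomes are momentary self-reports of affect, urge and cigarette count, which C2.5.1 itself describes as subjective. If some NRT participants know that they have nicotine, part of a lower reported urge or a lower cigarette count in that arm could come from expectation. For the mediation question (Aim 4.2), an expectancy effect on both startle and smoking could resemble mediation through the stress response. Without a record of what participants believed, the analysis could not tell these explanations apart.

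**Working it through.** The plan states no figure on this point, so there is none to reproduce. The check sets the statements in C2.4 side by side and then asks whether the size of the leak can be found.

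**1. Does the masking step reach the stamp?** The stamp is on the patch. The repackaging takes the patch out of its wrapper and puts it in a small bag. The wrapper's label goes and the stamp stays.

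**2. Who can learn what?**

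| Arm | What the participant sees | What can be inferred |
|---|---|---|
| NRT | Faint stamp naming nicotine and 21 mg | Active treatment, if the stamp is noticed and read |
| Placebo | Unmarked patch | Nothing directly; placebo only if the participant knows that active patches are stamped |

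The direct leak is in one arm only.

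**3. Can its size be found?** One patch a day for two weeks is up to 1 × 14 = 14 patches per person. Let p be the chance that the stamp is noticed on any one patch. The documents give no value for p, so the values below are assumptions.

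- If noticing were independent from day to day, the share who ever notice is 1 − (1 − p)^14.
- If noticing is wholly a trait of the person (someone who misses it once always misses it), the share is p.

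| Assumed p | Wholly person-level | Independent across 14 patches |
|---|---|---|
| 5% | 5% | 1 − 0.95^14 = 51% |
| 10% | 10% | 1 − 0.90^14 = 77% |
| 20% | 20% | 1 − 0.80^14 = 96% |

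The same person looks at the same mark each day, so independence is implausible and the right-hand column is an upper end. The result runs from 5% to 96% on assumptions that the documents cannot settle. The table shows only that the size is undetermined. It is not an estimate, and no headcount should be drawn from it.

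**4. Which analyses are exposed?**

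- *Most exposed:* the Aim 4 contrasts on EMA affect, urge and cigarettes, which are self-reported and compared by arm.
- *Less exposed:* startle potentiation (outcome of Aim 4.1, mediator in Aim 4.2) and abstinence checked by CO at the 2-week visit. Neither is a plain self-report. Still, startle is used as an index of anxiety, and CO cannot show why a participant abstained, so an expectancy effect is not ruled out.
- *Largely unaffected:* Aim 1 and the prediction tests of Aims 2 and 3, which do not rest on the contrast between arms.

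**5. Is there another safeguard?** Staff know the assignment, so masking of participants is the only masking left. No item measures whether it held.

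**The case against.** The strongest case for the plan has four parts.

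- **The plan discloses the difference and does not overclaim.** It calls the stamp faint and speaks of believability. It never describes participants as blinded. This stands. A reader might infer that the trial is simply not blind, or that most of the NRT arm would know its assignment. The documents support neither. They show only that masking is not secured for NRT participants who notice and read the print.
- **The leak runs one way.** Bias needs a difference in belief between arms. If most placebo participants believe that they have the active product, certainty among some NRT participants adds a smaller difference. This also stands, and the difference cannot be sized. The consent pages are not in the public document, so what participants were told about a placebo is unknown here.
- **Key measures are not self-reports.** Startle potentiation is the main laboratory measure, and smoking status is checked by CO. This narrows the concern to Aim 4 and chiefly to its EMA outcomes. The documents offer no evidence that expectancy moves startle, so for that measure it remains a possibility only.
- **Covering the stamp would not make the trial fully masked.** The placebo lozenge is a commercial mint, the risk section expects local skin reactions in up to 50% of patch users, staff are unblinded, and a sticker can be peeled off. All true. These points limit what the overlay can achieve, and they strengthen the case for asking participants what they think they received.

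None of this removes the stamp or supplies a measure of belief.

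**Conclusion.** The point holds in a limited form. The plan leaves a known mark on the active patch that identifies it, in the NRT arm only, and collects nothing that would show whether participants read it. An expectancy contribution to the Aim 4 arm contrasts can therefore be neither excluded nor assessed.

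The presence of the stamp and the absence of a masking step rest directly on C2.4. The number of participants affected and the resulting bias cannot be derived from the documents. The conclusion assumes only that the faint print can be read at handling distance. This should be fixed because the remedy is cheap, but it does not invalidate the trial.

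**What to change.** 1. **Cover the mark.** At the existing repackaging step, put the same opaque, neutral overlay on the same spot of the outer face of every active and placebo patch, after checking that it does not affect adhesion. Do not print a nicotine label on the placebo, since that would mislabel a nicotine-free product.
2. **Measure belief.** At the 2-week visit, ask every participant in both arms which treatment they think they received and why. The reason matters because it separates reading the stamp from guessing on the basis of taste, a skin reaction or perceived benefit. Report the answers by arm with the Aim 4 results. This step still helps if patches have already been handed out.
3. **State the limit.** Say in C2.4 and in the Aim 4 report that participant masking is incomplete, because the mint, skin reactions and unblinded staff remain as cues.

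The cost is some handling time per patch, one adhesion check and one extra questionnaire item with its reason. Sample size, visits and treatment are unchanged.
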